### 2.2.2. Nonclinical Toxicology of VOR

VOR has been investigated in nonclinical acute and oral repeated-dose toxicity studies, reproductive, developmental toxicity studies, and genetic toxicity studies to support oral administration of this compound to humans.

The main toxicities observed in animal models were weight loss and loss of appetite, apparent hemolytic anemia (rats only at 3.8 times the equivalent 400 mg human dose), leukopenia (rats only at 1.3 times the equivalent 400 mg human dose), thrombocytopenia (male rats only, statistically significant change at 0.5 times the equivalent 400 mg clinically effective human dose, but within normal range at all doses), and gastrointestinal tract irritation (dogs only, at 8.5 times the equivalent 400 mg human dose). Although statistically significant and dose-dependent, many of the clinical pathology findings were within normal historical ranges indicating that they should not have major toxicological consequences. The toxicities appeared to be rapidly reversible within 12 to 14 days. There has been no evidence of cardiac toxicity based on electrocardiogram (ECG, dogs only), blood pressure (dogs only), heart rate (dogs only), creatinine kinase, organ weight, gross pathology, or histopathology assessments in studies up to one month duration. No serious, irreversible damage to any vital organ has been observed. Importantly, toxicities in rats and dogs were predictive of adverse effects in humans (anorexia, weight loss, fatigue). Toxicities present in animals would be manageable in the clinic, and the onset of serious toxicity is readily forecasted by prodromal symptoms. The nonclinical toxicity profile of VOR is acceptable for an oncology drug.

### 2.2.3. Clinical Pharmacokinetics of VOR

The pharmacokinetics of VOR following 400 mg single-dose in a fasted state; and 400 mg single- and multiple-doses in a fed (high-fat meal) state were evaluated in 23 participants in a Phase I study with relapsed or refractory advanced cancer using a validated assay. VOR is eliminated predominantly through metabolism with less than 1% of the dose recovered as unchanged drug in urine, indicating that renal excretion does not play a role in the elimination of VOR. Recovery of two pharmacologically inactive metabolites, O glucuronide of VOR (OG-V) and 4 anilino-4 oxobutanoic acid (4A4OA), in urine was more substantial.

A population pharmacokinetic model using nonlinear mixed effects (NONMEM, ICON plc) demonstrated that a first-order, transit-compartment absorption and linear elimination best described VOR concentration data. The structural model was: (1)  $dX_a/dt = -K_a \times X_a$ , (2)  $dX_b/dt = K_a \times X_a - K_t \times X_b$ , (3)  $dX_c/dt = K_t \times X_b - (CL_t/V_c \times X_c)$ .

Fixed effects: CLt (731 L/h), Vc (5.21 L), Ka (1.35 1/h), Kt (0.7 1/h). Random effects: CLt (26% CV), Vc (76.8%), Ka (73%). Residual error was: 0.0001 ng/mL (additive), 73.6% (proportional). An exponential model was used for inter-individual variability; and a heteroscedastic model was used for residual variability. Weight (power model,  $Vctyp=Vcwt \times \text{Weight (kg)}^{\theta}$ ,  $\theta=1.17$ ) was found to be a significant covariate on Vc.

#### 2.2.4. Summary of Clinical Experience with VOR

VOR has been studied in Merck Research Labs (MRL) sponsored studies, Investigator Initiated Study Protocols (IISP) and National Cancer Institute (NCI) sponsored studies. VOR has been orally administered in Phase I, Phase II, and Phase III clinical studies in participants with advanced solid tumors and hematologic malignancies. VOR has been studied both alone and in combination with other chemotherapy agents. As of 02-Jul-2012, over 5,000 participants have received at least one dose of VOR in studies sponsored by Merck and Co., Inc., the NCI, or independent Investigators.

#### 2.2.5. Risks Associated with VOR

The types of adverse experiences observed in clinical trials of VOR in the oncology setting were those usually associated with chemotherapy, such as nausea, fatigue, diarrhea, constipation, and cytopenias. The three major clinical categories of adverse experiences attributable to VOR include a constellation of gastrointestinal symptoms, constitutional complaints, and cytopenias. All adverse experiences were manageable using conventional supportive care for chemotherapy. On the whole, treatment with oral VOR was well tolerated for use in the outpatient setting.

Merck & Co., Inc. sponsored VOR clinical studies showed that adverse experiences considered by the Investigators to be at least possibly related to VOR in  $\geq 10\%$  of participants included (in descending frequency): nausea, fatigue, diarrhea, anorexia, vomiting, thrombocytopenia, anemia, weight decreased, blood creatinine increased, dysgeusia, hyperglycemia, neutropenia, constipation. The total daily doses studied ranged from 200 mg to 900 mg. The tolerability of oral VOR appears to be determined by total daily dose and the length of consecutive days of dosing. The maximum tolerated dose (MTD) for continuous daily dosing without a rest period is 400 mg daily or 200 mg BID. The MTD for intermittent dosing is 300 mg BID  $\times$  3 consecutive days per week, or 250 mg TID  $\times$  14 consecutive days followed by a 7-day rest. Dose-limiting toxicities (DLTs) of single agent VOR were mainly non-hematologic (anorexia, dehydration, diarrhea, and fatigue); hematologic toxicities are primarily anemia and thrombocytopenia, most of which were mild to moderate. The majority of these DLTs occurred within the first month on oral VOR. The DLTs were manageable because the toxicities resolved quickly after drug administration was interrupted.

Dose-limiting toxicities (DLTs) have been mainly non-hematologic. The majority of these DLTs occurred within the first month on VOR. At continuous daily dosing of 600 mg QD, 300 mg BID, and 400 mg BID, doses that exceeded the established MTD, the pattern and severity of DLTs were similar. The DLTs were manageable because these toxicities resolved quickly after drug administration was interrupted. Hematologic events were primarily anemia, leukopenia, and thrombocytopenia. Generally, these events were rapidly reversible after study drug interruption.

Clinical serious adverse experiences (SAEs) regardless of causality have been reported in approximately 39% of the first 350 participants treated with VOR in Merck & Co., Inc. sponsored studies. This overall high incidence may reflect the underlying conditions of participants in this group. Of the participants who had a serious adverse experience, approximately 16% were considered by the Investigator to be related to study medication. Serious laboratory adverse experiences were uncommon, occurring in 3% or fewer of patients in the various populations. By contrast to patients with solid tumors, the incidence of SAEs was higher in patients with hematologic malignancies. Pulmonary embolism and deep vein thrombosis have been reported.

In prior studies, we assessed the intermittent administration of VOR to PLWH suppressed on ART. Thirty-two individuals received at least one 400 mg dose and thirteen received at least 10 doses of 400 mg (with up to 11 doses in one month), and we observed minimal side effects attributed to VOR. We observed no adverse events (AEs) exceeding Grade 1, but for a single episode of Grade 2 fatigue in one participant that resolved after 24 hours without intervention. No AEs led to the interruption of VOR dosing. We observed no new or unique AEs other than those commonly reported. Participants completing the combination VOR and HIV-specific ex vivo expanded T cells (HXTC) protocol will receive no more than a total of 4000 mg (2 cycles of 10 doses) of VOR. For reference, participants who completed our prior multi-dose studies under NIH U01 AI095052 received a total of 10,000 mg and 5200 mg of Vorinostat, respectively, without clear evidence of any durable drug-associated toxicity, and no AE greater than Grade 1.

In this proposed study, participants will receive 10 doses of 400 mg VOR over a 30 day period, then no VOR for 4 weeks. They will then receive a second cycle of 10 doses of 400mg VOR over another 30 day period, for a total of 20 doses. Each participant will receive a total of 5 HXTC infusions; 2 infusions will be administered in the first 4 week cycle and 3 administered in the second 4 week cycle. In our previous study with VOR, most participants exhibited a 15%–35% transient decline in platelet count after 4 weeks of 3 daily doses each week. However, only one participant's platelet count reached grade 1 toxicity level. No other clinical events or drug-related AEs were observed. Given we now propose to administer fewer doses, over a shorter time (20 doses over 3 months), significant toxicity seems unlikely.

### 2.2.6. Risk Associated with “unmasking” HIV

The HDAC inhibitors that “unmask” HIV in latent cells could cause other cells to become infected. However, we have not detected any evidence of this in the participants who received VOR thus far [73, 74]. We have observed a rare “blip” of low-level viremia; however, we have not observed any drug-resistance and/or failure of ongoing ART. Should we observe any instances of detectable HIV-1 RNA (> 50 copies/mL), we would repeat testing to confirm the result and inform all participants of the reason for re-testing. For those with confirmed viremia, we would notify the participant and their primary care provider for management per standard of care. If clinically indicated, blood samples would be obtained to measure antiretroviral serum drug levels and/or HIV phenotype and genotype to measure for the development of resistance. Participants with confirmed viremia > 150 copies/mL will be discontinued from the study.

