#### 3.1.3. Other Outcome Measures

- 3.1.3.1. Explore the influence of HXTC therapy combined with serial VOR doses on low-level plasma viremia as measured by single copy assay (SCA) in participants who maintained suppression on ART.
- 3.1.3.2. Explore the impact of VOR and HXTC therapy on the ability of CD8 T cells to enhance clearance of latently infected cells as they emerge from latency in a latency clearance assay.
- 3.1.3.3. Explore the impact of VOR and HXTC therapy on integrated proviral DNA quantification.
- 3.1.3.4. Explore the impact of VOR and HXTC therapy on the presence and persistence of T cell escape variants within the latent reservoir

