#### 3.2.2. Secondary

The secondary outcome will be the impact of VOR and HXTC therapy on the HIV-specific immune response and on the frequency of latent HIV infection, as measured by a QVOA and plasma HIV-1 RNA viremia measured by SCA, an assay with a limit of quantitation of 1 copy/mL.

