#### **5.4. Participant Withdrawal**

##### Handling of Participant Withdrawals or Participant Discontinuation of Study Intervention

Participants failing to meet criteria to advance to Step 4 are not required to complete an end of study visit (Step 6, Visit 23). Reasons for not progressing to Step 4 include:

- Inability to manufacture HXT product in Step 3
- Failure to meet requirements established for the pre-dose safety assessment for Step 4 at Visit 6.

If the participant withdraws, discontinues, or fails to advance in the study for any reason after initiating VOR dosing and HXT infusions in Step 4, the participant would be asked to complete an Early Discontinuation Study Visit (Step 6, Visit 23). This visit will occur  $\geq 4$  weeks but  $\leq 8$  weeks after the last documented visit or study treatment, whichever occurred last. Participants would then proceed to complete Visit 24.

In scenarios where participants are discontinued or withdrawn after receiving VOR doses in combinations with HXT infusions, the study PI (or designee) will make every effort to complete the Early Discontinuation Study Visit/End of Study Intervention (Step 6, Visit 23) evaluations.

The Early Discontinuation or End of Study Interventions Visit will include the clinical assessments and required labs per the SOE. The completion of the Leukapheresis procedure at this visit will be determined on a case-by-case basis by the study PI (or designee).

UNC reserves the right to discontinue the study for any reason at any time. The study may also be stopped if, in the opinion of the principal investigator and/or protocol team, the continuation of the study represents an unwarranted medical risk to the participants.

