## **5.5. Premature Termination or Suspension of Study**

### **5.5.1. Study Treatment Stopping Rules or Permanent Treatment Discontinuation**

A participant will not receive VOR and/or HXTc infusions if any of the following occurs:

- Pregnancy of study participant
- Treatment related  $\geq$  Grade 3 adverse event
- Requirement for prohibited concomitant medications
- Inability to complete treatments as defined in the protocol
- Request by participant to terminate study treatments
- Clinical reasons believed life-threatening by the PI or designee
- Hematologic dose-limiting toxicity defined as any confirmed toxicity  $\geq$  Grade 2, that cannot clearly be attributed to another reversible cause other than VOR
- Development of a dose-limiting toxicity
- HIV RNA  $> 150$  copies/mL on two consecutive determinations.

Participants who prematurely discontinue study treatment will move to Step 6, Visit 23 and will be followed through Visit 24. See section 5.4, Participant Withdrawal, for details on study procedures to be completed.

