## 7.5. Early Discontinuation Visit (Step 6, Visit 23)

Complete this visit any time a participant discontinues early from the study. This is the End of Study Intervention Visit and completed when participants complete study interventions, whether pre-maturely (as with an early discontinuation or upon successful completion of the study).

Perform the Early Discontinuation or End of Study Intervention Visit assessments and procedures per the SOE.

The Leukapheresis is completed on all participants who have completed all dosing visits. If a participant terminates early, completion of the leukapheresis at Visit 23 will be determined by study PI or the study team.

Estimated Blood Volume: up to 65 mL

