#### 10.7.2. Secondary Analysis

The virologic analysis will include comparison of the SCA levels pre-treatment (screening and entry) compared to post-treatment in Steps 5 and 6. We assume that the probability would be 0.10 (10%) for a baseline (pre-entry, entry) detectable SCA  $\geq 1$  copy and the probability would be at least 0.29 (29%) for a post-treatment measure for analyses. The assumption that 10% of participants with a quantifiable SCA at screening will have SCA below the limit of detection at a pre-treatment

measure is an estimate based on data from A5244 in which 6 of 50 (12%) enrolled participants had undetectable SCA at pre-entry and 5 of 51 (10%) at entry after having a screening SCA  $\geq 1$  copy [65].

For additional secondary endpoints, most endpoints are defined as change in a quantitative measure from baseline to post-infusion (e.g., change from baseline to week 13 in HIV-1 RNA by SCA). Assuming two-sided 0.05 significance, 5000 empirical simulations from a normal distribution with mean change equal to 1 standard deviation with n=12 evaluable participants achieved 85% power to detect a statistically significant change from baseline to post-infusion using an exact Wilcoxon signed-rank test (paired data). Thus, with n=12 there is reasonable power to detect a mean change of 1 standard deviation (SD) or larger. Observed virologic measurements may not be normally distributed or may be partially censored due to assay limits of quantification, and thus, an exact Wilcoxon signed-rank test will be used. Potential immune correlates of antiviral impact will be assessed via exact, non-parametric Spearman rank correlation based methods.

Descriptive statistics and graphical data displays will be used to summarize in vivo measurements of HIV-specific T-cells over the pre- to post-infusion period to assess the pattern and magnitudes of T-cell expansion and persistence for each virus. Measurements of immunity will be evaluated by descriptive statistics at each time point and analyzed by exact, nonparametric methods for paired data to compare changes from pre- to post-infusion. HIV-1 specific immune responses using standard immunoassays and measures of HIV-1 persistence will be analyzed similarly.

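### The plan gives two consequences for confirmed viremia above 150 copies/mL, and its SCA objective, read literally, covers only participants who stayed suppressed, so a rise on treatment can be left out of the viremia comparison

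*Combined protocol and SAP*

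**What the plan says.** **Consequence of viremia.** Section 2.2.6, on the risk of unmasking latent virus, states: "Participants with confirmed viremia > 150 copies/mL will be discontinued from the study". Section 5.5.1 lists the same threshold, on two consecutive determinations, among the reasons to withhold VOR and/or HXTC, and continues: "Participants who prematurely discontinue study treatment will move to Step 6, Visit 23 and will be followed through Visit 24". Section 5.5.2, which lists reasons for leaving the study, does not include viremia.

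**Visits after early discontinuation.** Section 5.4 covers anyone who has started Step 4: "If the participant withdraws, discontinues, or fails to advance in the study for any reason", that person is asked to complete Visit 23 and then Visit 24. Section 7.5 says of Visit 23: "Complete this visit any time a participant discontinues early from the study". Sections 7.3.5.3 and 9.3 agree. Leukapheresis at that visit is decided case by case (5.4, 7.5).

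**SCA endpoint.** Objective 3.1.3.1, repeated in the Protocol Summary, concerns "low-level plasma viremia as measured by single copy assay (SCA) in participants who maintained suppression on ART". Section 3.2.2 names, as part of the secondary outcome, "plasma HIV-1 RNA viremia measured by SCA, an assay with a limit of quantitation of 1 copy/mL", with no population limit. Section 10.7.2 states: "The virologic analysis will include comparison of the SCA levels pre-treatment (screening and entry) compared to post-treatment in Steps 5 and 6". It defines no SCA analysis set and has no rule for a viremic or discontinued participant. Section 10.4 replaces any participant not given the full study treatment.

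**The concern.** A latency-reversing drug could raise plasma viremia, and 2.2.6 names this kind of risk. The SCA endpoint should therefore be able to show movement in either direction. If participants with a confirmed rise can be left out because they did not keep suppression, the analysis set depends on the outcome being measured. The exclusions run in one direction only, so the pre/post comparison leans toward a fall.

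Replacement under 10.4 can worsen this: a participant stopped during dosing for viremia is not fully treated and can give way to a new participant. Since 10.6 aims for 12 participants with evaluable data, one person carries real weight.

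**Working it through.** **Step 1. Set the passages side by side for confirmed HIV RNA >150 copies/mL.**

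| Section | Consequence |
|---|---|
| 2.2.6 | Off study |
| 5.5.1 | Treatment stopped; Visit 23, then through Visit 24 |
| 5.5.2 | Viremia not listed as a reason to leave the study |
| 5.4, 7.3.5.3, 7.5, 9.3 | Early discontinuers after the start of Step 4 are sent to Visit 23; 5.4, 7.3.5.3 and 9.3 add Visit 24 |

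The Schedule of Events places HIV-1 RNA at Visits 21, 23 and 24, and SCA at Visits 21 and 23. So a Visit 23 HIV RNA and SCA sample may exist under either rule. IUPM is less certain, because the leukapheresis is discretionary. The main route to loss is the suppression condition in 3.1.3.1, with no analysis set in 10.7.2 and replacement in 10.4.

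**Step 2. Reproduce the plan's figure.** Section 10.7.2 gives 85% power for the exact Wilcoxon signed-rank test with n=12, mean change 1 SD and two-sided 0.05. The exact two-sided p is 2 × (number of subsets of ranks 1 to n with sum ≤ W) / 2^n, where W is the smaller rank sum. For n=12 the critical value is W ≤ 13: 2 × 87/4096 = 0.0425. Simulating 200,000 trials gives 85.2%, so the figure reproduces and is not in dispute.

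**Step 3. Effect of leaving out one viremic participant.** The counts are assumed. In each row W is the rank sum of the rises.

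| Pattern | Rise(s) kept, n=12 | Dropped |
|---|---|---|
| 11 falls, one rise at rank 12 | W=12: 2×70/4096 = 0.034 | n=11, W=0: 2×1/2048 = 0.001 |
| 10 falls, rises at ranks 12 and 3 | W=15: 2×131/4096 = 0.064 | rank 12 dropped, n=11, W=3: 2×5/2048 = 0.005 |
| 10 falls, rises at ranks 12 and 11 | W=23: 2×478/4096 = 0.233 | both dropped, n=10, W=0: 2×1/1024 = 0.002 |

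The top rank is plausible on the copies/mL scale. Entry requires HIV RNA below 50 (5.1.8), so a fall is smaller than 50, while a rise past 150 exceeds 150 − 50 = 100. This assumes that the SCA sample is taken while the person is viremic. On a log scale the top rank is not guaranteed; 10.7.2 does not state the scale.

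**Step 4. False-positive rate with no true change.** Simulating 12 normal changes centred on zero, the chance of a nominally significant decrease is 2.1% with all kept, 7.2% if the largest upward change is dropped, and 17.3% if the two largest are dropped. This supposes that an exclusion happens in every trial, so it shows direction and potential size, not an expected rate.

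**Step 5. Power if those dropped are not replaced.** At a 1 SD change, power is 81% with n=11 and 79% with n=10.

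**The case against.** **The follow-up provisions limit the damage.** A reader might infer from 2.2.6 that a viremic participant has no Visit 23 data. The documents do not support that: 5.4, 7.3.5.3, 7.5 and 9.3 send early discontinuers to the closing visits whichever label is used. Virologic failures are also monitored monthly and the monthly data shared with the safety monitoring committee (10.5). This part of the objection stands.

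**The suppression phrase may only describe who was enrolled.** Neighbouring objectives speak of participants maintained on suppressive therapy, and 10.7.2 excludes nobody for viremia. The text does not settle the matter. But the wording of 3.1.3.1 differs from its neighbours and literally describes a result, so an analyst could defend the exclusion.

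**Not every rise is removed.** A reader might infer that only people without a rise are analysed. That is wrong: the trigger is confirmed HIV RNA >150 copies/mL, whereas SCA quantifies to 1 copy/mL. Rises within the suppressed range stay in.

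**One exclusion need not change the conclusion.** With 11 falls and one top-ranked rise, the test is significant either way. Crossing 0.05 in the second pattern needs another assumed riser. Section 2.2.6 reports only rare low-level blips and no failure of ongoing ART.

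**A rise may reflect missed ART.** Poor adherence is itself a withdrawal reason in 5.5.2. Scoring every such participant as the largest increase would attribute the rise to study treatment, so that scoring belongs in a sensitivity analysis.

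**Conclusion.** The concern holds in a limited form. Sections 2.2.6 and 5.5.1 give different consequences for one event and must be reconciled; which clinical rule applies is for the sponsor. Separately, the literal wording of the SCA objective, the lack of an SCA analysis set in 10.7.2 and the replacement rule in 10.4 together allow a participant with a treatment-related rise to be left out of the viremia comparison. Any resulting bias is toward an apparent fall.

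Its size depends on assumed counts, since the plan gives no expected rate of confirmed viremia. One excluded top-ranked rise moves p from 0.034 to 0.001 in one pattern and from 0.064 to 0.005 in another. The stronger readings, that all post-treatment data are lost or that a single case always reverses the result, are not supported. SCA is not a primary endpoint: it is an other outcome in 3.1.3 and a secondary one in 3.2.2.

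**What to change.** 1. Reconcile 2.2.6, 5.5.1 and 5.5.2 so that they state one consequence for study follow-up after confirmed HIV RNA >150 copies/mL.
2. In the Protocol Summary and 3.1.3.1, delete the condition on having kept suppression, or reword it so that it plainly describes the population at enrollment.
3. In 10.7.2, state that SCA is analysed in all dosed participants with a baseline value, including those discontinued or replaced, using their Visit 23 sample. Naming the visit matters because the example in 10.7.2 uses week 13, which is Visit 21, while 5.5.1 moves those who stop treatment to Visit 23.
4. Add a sensitivity analysis that ranks a participant with confirmed HIV RNA >150 copies/mL and no later SCA as the largest increase.

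The cost is protocol and analysis wording only; no new visits or samples are needed. The SCA result may look slightly less favourable.
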